10.9 Reporting Serious Unexpected Suspected Adverse Reactions (SUSARs)

In-line with the Medicines for Human Use (Clinical Trials) Regulations 2004, all relevant information about adverse drug reactions to the investigational medicinal product (LIRA 3mg, Saxenda®) in the proposed study, that are both serious and unexpected, will be subject to expedited recording to the appropriate Regulatory Authority and Research Ethics Committee (REC).

The University of Leicester, as Sponsor, will report all the relevant safety information previously described to the concerned competent authorities and to the Research Ethics Committee concerned. The Sponsor will inform all investigators concerned of relevant information about SUSARs that could adversely affect the safety of participants.

A SUSAR that is fatal or life threatening will be reported to the relevant regulatory authority (MHRA/HPRA) and main REC within 7 working days after University of Leicester, the study Sponsor or their delegate becomes aware of the event. In each case relevant follow-up information will be sought and a report completed as soon as possible. It will be communicated to the MHRA/HPRA and the Ethics Committee within an additional eight calendar days.

A SUSAR that is not fatal or life threatening will be reported to the relevant regulatory authority (MHRA/HPRA) and main REC within 15 working days after the University of Leicester, the study Sponsor or their delegate becomes aware of the event. Further relevant follow-up information will be given as soon as possible.

Information on the final description and evaluation of an adverse reaction report may not be available within the required time frames for reporting. For regulatory purposes, initial expedited reports will be submitted within the time limits as soon as the minimum following criteria are met:

- a suspected investigational medicinal product,
- an identifiable subject (e.g. study subject code number),
- an adverse event assessed as serious and unexpected, and for which there is a reasonable suspected causal relationship,
- an identifiable reporting source and, when available and applicable a unique clinical trial identification (EudraCT number).

In case of incomplete information at the time of initial reporting, all the appropriate information for an adequate analysis of causality will be actively sought from the reporter or other available sources. The University of Leicester, the study Sponsor or their delegate will report further relevant information after receipt as follow-up reports.

In certain cases, it may be appropriate to conduct follow-up of the long-term outcome of a particular reaction.

Electronic reporting will be the expected method for expedited reporting of SUSARs to the MHRA/HPRA. In that case, the format and content as defined by the Guidance 1 will be adhered to.

10.10 Reporting of Adverse Events to Novo Nordisk

Adverse events related to the Novo Nordisk drug might potentially disclose important safety information. The investigator should copy Novo Nordisk into all communications when expediting SARs or SUSARs to the Sponsor, health and regulatory authorities and should report all SAR's related to Novo Nordisk's product (LIRA 3mg, Saxenda®) to the local Novo Nordisk affiliate safety department. The submission to Novo Nordisk must be within 15 days from the Investigator's first knowledge about a valid case.

Therefore all UK cases will be reported to the UK affiliate Novo Nordisk UK on:
[contact]
[contact]
Email: [contact]

All Ireland cases will be reported to: [name], Clinical Medical & Regulatory Manager
Phone no: ([contact]
Fax no: Tel: ([contact]
Email: [contact]

The following events will be reported to Novo Nordisk:

- A. Serious Adverse Reaction or Suspected Unexpected Serious Adverse Reactions: as described in section 10.1.
- B. Serious Adverse Drug Reaction: An adverse drug reaction (ADR) is an adverse event for which a causal relationship (Possible/Probable relation) between the Novo Nordisk drug and the occurrence of the event is suspected. The ADR should be classified as serious if it fulfils one or more of the seriousness criteria (www.wikipedia; search: emea seriousness criteria)
- C. Pregnancies: where a foetus or embryo has been potentially exposed to the Novo Nordisk product. The outcome of such pregnancies must be reported and the child followed up for a period of 1 month after birth with any Adverse Events regarding the child reported.

For any of these events the following parameters must be recorded as a minimum:

- Study name
- Patient identification (e.g. initials, sex, age)
- Event (preferably a diagnosis)
- Drug (e.g. Saxenda)
- Reported identification (e.g. Name, or initials)
- Causality
- Outcome

All events should be recorded by the Investigator on standardised forms as follows:

- Serious Adverse Event Form (for SAE/SADR Safety Information)
- Pregnancy Form Part A

Serious ADRs follow special reporting procedures as follows:

- Initial information must be forwarded to Novo Nordisk within 24 hours of obtaining knowledge about the serious ADR.
- Completed forms must be forwarded electronically/fax/courier within 5 calendar days of obtaining knowledge about the serious ADR.

In addition to the above the reporting of SAE/SADR should also be submitted to local authorities according to national requirements.

11 STATISTICS

11.1 Statistical methods and analysis

A CONSORT diagram showing the flow of participants through the study will be produced. Baseline characteristics of the participants will be summarised by group using mean (standard deviation), median (interquartile range) or count (percentage) as appropriate.

The primary analyses will compare the proportion of participants achieving $\geq 15\%$ weight loss at 52 weeks (primary outcome) after randomisation between the two study groups using a logistic regression model with adjustment for the stratification factors (site and BMI). The adjusted proportion (95% confidence interval) of participants achieving $\geq 15\%$ weight loss will be estimated by group. The primary analyses will be based on the complete cases population, with intention to treat (ITT) and per protocol analyses as secondary analyses (see Sections 11.3 and 11.5). In all analyses, participants will be analysed in the group to which they were randomised at baseline; importantly, the participants in the intervention group who stop LIRA 3mg, because they meet a pre-specified stopping rule, will still be analysed in the intervention group. Participants who have undergone bariatric surgery during the period of the study will be excluded from the analysis for the primary outcome, because these participants are likely to have substantial weight loss, but are unlikely to be balanced between the groups (as it is expected that fewer participants in the intervention group will require bariatric surgery due to their expected weight loss). Missing primary outcome data will need to be imputed for the ITT analyses; this will be done by assuming that these participants did not achieve $\geq 15\%$ weight loss at 52 weeks, which is a conservative approach. The characteristics of those with missing outcome data will be compared with those who have completed follow-up. The complete cases, ITT, and per protocol analyses will compare the two groups to demonstrate the effectiveness of the targeted prescribing pathway compared with standard care.

Secondary outcomes measured at 52 weeks and 104 weeks will be analysed in a similar way, with binary outcomes compared using logistic regression models and summarised using proportion (95% confidence interval), and continuous outcomes compared using linear regression models and summarised using mean (95% confidence interval). If continuous outcomes are non-normally distributed then they will be transformed or a more suitable regression model will be selected. In all analyses, participants will be analysed in the group to which they were randomised at baseline. Only the complete cases population will be used for the secondary outcomes to reduce the number of models being fitted. Participants who have undergone bariatric surgery during the period of the study will be excluded from these analyses. Data on treatment adherence, safety (including adverse events), and treatment satisfaction will be summarised and tabulated.

As additional secondary analyses, we will perform a responder analysis which will repeat the analyses of the secondary outcomes with the intervention group restricted to those participants who responded to the targeted prescribing pathway (i.e. had achieved $\geq 15\%$ weight loss at 52 weeks after randomisation). The purpose of these analyses is to compare the outcomes of “early and good” responders to the targeted prescribing pathway with those who received standard care only. Therefore, all participants randomised to the standard care group will also be included in these responder analyses.

11.2 Sample Size

Based on previous studies, it is expected that at one year approximately 5% of the participants in the standard care group will have achieved $\geq 15\%$ weight loss (likely range: 3%-5%) [5, 7]. An achievable target for $\geq 15\%$ weight loss at one year in the intervention group is 16% (likely range: 14%-20%) [5,7]. Based on these proportions, 25% drop out, 5% alpha and a 2:1 randomisation ratio with the higher proportion of participants being randomised to the intervention group, we would need to recruit 392 participants (261 intervention group; 131 standard care) to have 80% power to detect a significant difference between the groups at one year. With 261 participants randomised to the intervention group, and based on 16% achieving $\geq 15\%$ weight loss at 12 months, an estimated 40 participants in the intervention group will be eligible for the responder analyses. All 131 participants in the standard care group will be eligible for the responder analyses.

11.3 Missing/unused/spurious data procedure

Attempts will be made to assess the primary outcome on all participants including those who have withdrawn from treatment. The number of missing observations for each outcome will be reported. If missing outcome data are present then the initial analysis will be based on the complete cases. A sensitivity analysis will then be carried out repeating the analyses with the ITT population to assess the possible impact of the missing data on the results produced. Missing primary outcome data will need to be imputed for the ITT analyses; this will be done by assuming that these participants did not achieve $\geq 15\%$ weight loss at 52 weeks, which is a conservative approach. We will also attempt to address bias by comparing the characteristics of those with missing outcome data to those who have completed follow-up. This strategy for dealing with missing outcome data has been recommended by White et al. [9].

11.4 Disposition of Patients

Screened patients

Screened patients are defined as any patient who met the inclusion criteria and signed the informed consent form.

Treated patients

Treated patients consist of all patients, who have been allocated to one of the two treatment groups, and have at least partially completed the Baseline Visit.

Data from all randomised participants will be used in the study final report and analysis, with data analysed in the group to which the participant was randomised. Participants who have undergone bariatric surgery during the period of the study will be excluded from the complete cases, per protocol and responder populations.

11.5 Analysis Populations

Complete cases population

The complete cases population is defined as all randomised participants who have data available for the outcome being analysed, according to the study group to which they were randomised at baseline. Participants who had bariatric surgery during the study period will be excluded from this population.

ITT population

The ITT population are all randomised participants and they will be analysed according to the treatment group to which they were randomised at baseline. Missing outcome data will be imputed. Participants who had bariatric surgery during the study period will be included in this population.

Per protocol population

The per protocol population is defined as all participants who were compliant with their randomised treatment group, analysed according to the treatment group to which they have randomised at baseline. Participants in the standard care group are defined as treatment compliant if they complete at least 70% of the planned contacts in the Tier 3 service. Participants in the intervention group are defined as treatment compliant if they complete at least 70% of the planned contacts in the Tier 3 service, and take at least 70% of their planned doses of LIRA 3mg as stipulated by the prescribing pathway. Participants who had bariatric surgery during the study period will be excluded from this population.

Responder population

The Responder population is defined as all participants in the intervention group who achieved $\geq 15\%$ weight loss at 52 weeks, and all participants in the standard care group. Participants will be analysed according to the treatment group to which they were randomised at baseline. Participants who had bariatric surgery during the study period will be excluded from this population.

11.6 Health Economic Input

A state-transition Markov cohort model has been developed, with health states encompassing the possible co-morbidities associated with obesity and documented to respond to weight loss. A thorough review of the literature was conducted to identify such conditions and inform transition probabilities in the model.

The model projects development of T2DM, myocardial infarction (MI), stroke, asthma, cancer or mortality in the long term (up to lifetime horizon) based on short term effects of interventions in surrogate outcomes – body mass index (BMI), systolic blood pressure (SBP), total cholesterol, high-density lipoprotein (HDL) cholesterol and (for patients with T2DM) glycated haemoglobin (HbA1c). Effects on surrogate outcomes are translated into lifetime risks through risk-prediction models.

Treatment effects are applied incrementally to the efficacy of the targeted prescribing pathway group. Effect on weight, in terms of BMI % reduction, is applied at every subsequent cycle starting from 3 months after treatment start for as long as the cohort remains on treatment and over the predefined catch-up time post-treatment. Note that a natural increase in weight is applied each year to all interventions considered, including no treatment.

Treatment can be discontinued at 16 weeks, 32 weeks [note: the current version of the model does not include the functionality for a 32 week stopping rule, but that will be added] (based on the pre-specified stopping rule) or at 52 weeks. Discontinuation at 3 months causes the cohort to move to the control group, and subsequently follow the clinical pathway of this treatment group who will be

receiving the standard care providing via the Tier 3 service. Thus, if the discontinuation is allowed at 16 weeks, non-responders will have the same effect of the cohort in the control group, and responders will have the effect of the targeted prescribing pathway in the clinical trial.

Discontinuation beyond 52 weeks causes BMI, and other cardio-metabolic risk factors, to revert to the levels projected under the no treatment option. Reversal takes place over a given number of cycles (years) – catch-up time – as defined by the user. Costs and quality of life outcomes are applied to the health state in which the cohort resides at each particular moment in time or once-off to events. Costs and health benefits (life years, quality-adjusted life-years, years T2DM free, years cancer free etc.) are summed-up for the time horizon of the model and results reported as incremental cost-effectiveness ratios. The risk of acquiring obesity-related co-morbidities have been taken from published epidemiological studies.

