The majority of the trials involving LIRA 3mg have been placebo controlled, have included patients with BMI as low as $27\text{ kg}/\text{m}^2$, and have all continued LIRA 3mg treatment from the start of treatment for up to 3 years, irrespective of individual effectiveness, even for patients who fail to lose any weight [5-7]. Best clinical practice would suggest that patients who fail to lose weight should not be continued on treatment because they are exposed to increased risk of adverse effects without significant benefit in terms of weight loss. Moreover, being randomised, with the uncertainty as to whether an active agent is being given, is a disincentive to compliance with diet and exercise advice for some patients. Effect sizes may be affected by the strict protocols of an RCT and these data may not be optimal for health economic analyses as real-world applicability and generalisability of RCTs are limited. Nonetheless, within the populations studied, LIRA 3mg resulted in $\geq 15\%$ weight loss in 14% of patients, compared with 3.5% of patients with placebo [5], a reduction which is likely to generate major health benefits and long-term cost-savings, especially if weight loss can be maintained [7]. Among obese patients with T2DM, weight loss is less, but the potential cost-savings are greater [6].

Post-hoc analysis of the SCALE Obesity trial comparing “early responders” (lost $\geq 5\%$ of their starting weight after 16 weeks of LIRA 3mg treatment) with “early non-responders” (lost $< 5\%$ of their starting weight after 16 weeks of LIRA 3mg treatment) found that 24.2% of early responders had lost $\geq 15\%$ of their bodyweight at 56 weeks compared with 1.8% of early non-responders [8]. A different model for the use of LIRA 3mg has been suggested by the SCALE Maintenance study which required a substantial weight loss ($\geq 5\%$ of the baseline weight) with lifestyle changes (including meal replacement strategies) during a period of 12 weeks prior to commencing the drug. The study resulted in 26% of patients achieving $\geq 15\%$ weight loss one year after treatment with LIRA 3mg compared with 6% of patients on placebo [7]. Overall, these results suggest that the patients who are more likely to achieve clinically significant long-term weight loss with LIRA 3mg are those who achieve $\geq 5\%$ weight loss during the first 12-16 weeks either with lifestyle changes or with LIRA 3mg treatment.

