- b) compare long-term maintenance between the two groups, by comparing the proportion of participants maintaining weight loss of $\geq 15\%$ at 104 weeks among those who achieved $\geq 15\%$ weight loss at 52 weeks
- c) evaluate the budget impact and cost-effectiveness of the targeted prescribing pathway over the 104 weeks of the study.

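### The cost-effectiveness model's week-16 responder split does not in general reproduce the randomised contrast, and Protocol 11.6 does not say which effect responders receive

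*Protocol*

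**What the plan says.** Protocol section 11.6 describes a Markov cohort model that projects short-term trial effects over a horizon of up to a lifetime. Its weight input is a percentage change in BMI: "Effect on weight, in terms of BMI % reduction, is applied at every subsequent cycle starting from 3 months" after treatment start. On stopping, it says "Treatment can be discontinued at 16 weeks, 32 weeks" or at 52 weeks. For the week-16 decision it says that "non-responders will have the same effect of the cohort in the control group, and responders will have the effect of the targeted prescribing pathway", as seen in the trial. The condition attached to that sentence, that stopping at 16 weeks is allowed, is met by the first stopping rule in section 6.2.

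The section also says that "Discontinuation at 3 months causes the cohort to move to the control group". On the second stopping rule it notes that "the current version of the model does not include the functionality for a 32 week stopping rule, but that will be added".

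The effectiveness analysis takes a different approach. Under section 11.1, intervention participants "who stop LIRA 3mg, because they meet a pre-specified stopping rule, will still be analysed in the intervention group". The SAP (sections 1 and 1.1.3) leaves health economics to separate work, so section 11.6 is the only specification of the model in these documents.

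**The concern.** Participants who miss the week-16 target are selected for a poor early course. The control cohort is not selected: it includes people who would have lost weight early in any case. Giving the first group the average of the second replaces an observed outcome with a different one.

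The responder half is ambiguous. The effect of the pathway in the trial could mean the average over the whole intervention arm, which already contains the non-responders, or the effect seen in responders alone. The two lead to different models, and the section does not choose between them.

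Long-term cost-effectiveness is a named secondary objective, and the input effect is carried forward for up to a lifetime into incremental ratios. An error at the trial-period stage is therefore carried forward too, although the trial will hold the randomised data needed to avoid it.

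**Working it through.** **Notation.** r is the share of the intervention arm that responds at week 16. R and NR are the one-year outcomes of intervention-arm responders and non-responders. T = rR + (1 − r)NR is the whole intervention arm, and C is the whole control arm. The randomised contrast is T − C.

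**Algebra.**
- Whole-arm reading (responders receive T): modelled arm = rT + (1 − r)C, so modelled contrast = r(T − C). This is too small for any r below 1 and any positive effect.
- Responder-specific reading (responders receive R): modelled arm = rR + (1 − r)C, so error against T = (1 − r)(C − NR). This is zero only if NR = C (or everyone responds).

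Both results hold for proportions and for means.

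**Plan's own figures.** Section 11.6 gives no numerical result to reproduce. The planning rates in section 11.2 (5% v 16%, two-sided 5% alpha, 2:1, 80% power) give 96 controls and 288 in total. Allowing for 25% dropout, 288/0.75 = 384, against 392 stated. The sample size does not depend on the model.

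**Inputs for the illustration.** All are proportions losing at least 15% of body weight.
- T = 14%, C = 3.5%: the cited placebo-controlled trial, Protocol section 4. Section 14.10.2 gives its placebo rate as 3%; the planning control rate in section 11.2 is 5%.
- R = 24.2%, NR = 1.8%: the cited post-hoc analysis by week-16 response, section 4 ("24.2% of early responders had lost" that much at 56 weeks).
- Assumption: these figures describe one population.

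**Results.**
1. Responder share: r = (14 − 1.8)/(24.2 − 1.8) = 12.2/22.4 = 0.5446, about 54%.
2. Randomised contrast: 14 − 3.5 = 10.5 points.
3. Whole-arm reading: 0.5446 × 14 + 0.4554 × 3.5 = 9.2%. Contrast 9.2 − 3.5 = 5.7 points, which is 46% too small.
4. Responder-specific reading: 0.5446 × 24.2 + 0.4554 × 3.5 = 14.8%. Contrast 14.8 − 3.5 = 11.3 points. The error is 0.4554 × (3.5 − 1.8) = 0.8 points, about 7% too large.

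Varying the control rate over the values in the protocol:

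| C | Randomised contrast | Whole-arm reading | Responder-specific reading |
|---|---|---|---|
| 3% | 11.0 | 6.0 | 11.5 (+0.5) |
| 3.5% | 10.5 | 5.7 | 11.3 (+0.8) |
| 5% | 9.0 | 4.9 | 10.5 (+1.5) |

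At the planning rates (16% v 5%), with r assumed between 0.4 and 0.7, the whole-arm reading turns 11 points into 0.4 × 11 = 4.4 to 0.7 × 11 = 7.7 points.

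**The case against.** The strongest reply is that section 11.6 summarises a model that is still being changed and is to be documented elsewhere. One ambiguous sentence does not show how the model is parameterised, and the lack of a stated check against the arm means does not show that none exists. Moreover, participants stopped at week 16 then receive the same Tier 3 care as controls, so giving them the control course is a recognisable simplification. If responders receive their own effect and non-responders do equal control, the rule returns the randomised contrast exactly.

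Most of this stands as a limit on what can be claimed:
- A reader might infer that neither reading can ever match the randomised difference. That is too strong, because of the special case just given. The protocol's proxy figures do not support that case, however: 1.8% in early non-responders against 3.5% on placebo.
- A reader might infer that cost-effectiveness is biased in a known direction. The documents do not support this, since the two readings err in opposite directions.
- A reader might infer that the model would show a benefit from an inert drug. On the responder-specific reading that follows if early and later weight loss are positively correlated. Its size, though, needs means, SDs and a correlation that the documents do not give, and the cited trial shows a real difference.
- A reader might tie the point to the aim to "evaluate the budget impact and cost-effectiveness of the targeted prescribing pathway over the 104 weeks of the study". The rule belongs to the long-term projection, so secondary objective 5 is the clearer anchor.

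The reply does not remove the need to act. The rule is written in the protocol, nothing else in these documents qualifies it, and one permitted implementation loses nearly half the effect on the illustrative figures.

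**Conclusion.** The concern holds in a limited form. The split in section 11.6 returns the randomised contrast only if responders are given their own effect and non-responders match the whole control arm. The first condition is not stated, and the second is not supported by the protocol's own cited figures.

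The illustrative size, 5.7 or 11.3 points against 10.5, rests on three assumptions: that the overall and response-specific rates come from one population; that a trial which continued treatment regardless of response can stand in for a pathway with stopping rules; and that the proportion losing at least 15% is an adequate proxy for the model's BMI input. The documents give no responder or non-responder values for BMI or the other risk factors, so the effect on QALYs, costs or the incremental ratio cannot be derived.

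The primary outcome, the SAP analyses and the sample size are unaffected. The mismatch between 3 months and 16 weeks is an inconsistency within the section, with no numerical consequence shown.

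**What to change.** - For the trial period, drive the model from the observed randomised arm means: all intervention participants, including those stopped under a rule, against all controls.
- If the model must split by response, give each intervention-arm subgroup its own observed trajectory, so that the weighted sum returns the arm mean at 52 and 104 weeks. Report that check.
- State in section 11.6 which effect responders receive.
- Apply the same principle to the 32-week rule when it is added.
- Keep the assumption that non-responders equal control as a sensitivity analysis only.
- Reconcile the references to 3 months and 16 weeks in section 11.6.

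The cost is re-parameterising a model that is already due to change, before the economic analysis is run. No new data are needed.
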